3.2 Benefits Analysis

* Describe any potential benefits of the proposed research to the participants. If there are no benefits, state this explicitly:

The patient centred evidence-based perioperative program that participants will be undertaking has the potential to: 1) improve post-surgical pain; 2) increase post-surgical functional and patient oriented outcomes; 3) decrease post-surgical opioid use; and 4) decrease short- and long-term

healthcare costs by reducing readmissions, and post-operative health utilization.

2.0 * Describe the scientific and/or scholarly benefits of the proposed research:

This study is novel and timely given the current healthcare focus on improving prevention strategies, and improving access to, delivery and outcomes of surgical interventions. This will be the first perioperative program specifically developed for patients undergoing surgery for inguinal hernia. The obvious potential benefits for patients undergoing inguinal hernia repair is the development of a program that has the potential to improve post-surgical outcomes, increase quality of life, while addressing healthcare and individual costs, minimizing the impact of the condition on the individual and society.

3.0 If this research involves risk to participants explain how the benefits outweigh the risks.

While the perioperative program comes with some inherent risks due to participation in exercise, this exercise also comes will several potential benefits for participants. Since the risk of adverse events are quite small, we believe the potential benefits outweigh the risks.

4.1	Par	ticipa	ant Int	forma	ation
-----	-----	--------	---------	-------	-------

1.0	* Will you be recruiting human participants (i.e. enrolling people into the study, sending people online surveys to complete)? Yes No
	1.1 Will participants be recruited or their data be collected from Alberta Health Services or Covenant Health or data custodian as defined in the Alberta Health Information Act? Yes No
	1.2 Would you like to include information about this study on the Be The Cure searchable database? Yes No

4.2 Additional Participant Information

1.0 Describe the participants that will be included in this study. Outline ALL participants (i.e. if you are enrolling healthy controls as well):

We will recruit 30 participants with inguinal hernia who are scheduled for surgery by a general surgeon in Fort Saskatchewan ([name]). We will recruit 30 participants in total and randomize 15 participants to each of the intervention and control groups.

* Describe and justify the inclusion criteria for participants (e.g. age range, health status, gender, etc.):

Inclusion criteria include:

- 1) scheduled to undergo first-time inguinal hernia repair surgery after a physical examination identified signs and symptoms consistent with inguinal hernia (direct or indirect hernia);
- 2) willingness to participate in a 6-week targeted exercise program;
- 3) 18+ years of age;
- 4) no medical contraindications to participation in exercise. Contraindications that will be screened for include associated medical conditions that preclude exercise. This includes uncontrolled medical conditions including diabetes, hypertension, vertigo, congestive heart failure, chronic obstructive pulmonary disease, intra-abdominal ascites, or pre-existing malnutrition.

and

5) employed full-time and required to lift at least 10kg at work.

3.0 Describe and justify the exclusion criteria for participants:

Exclusion criteria include: 1) previous inguinal hernia;

- 2) Body Mass Index >35 since morbidly obese patients experience more surgical complications
- 3) use of narcotics
- 4) bone and joint conditions of the spine or extremities
- 5) history of other abdominal surgeries

4.0 Participants

4.1 How many participants do you hope to recruit (including controls, if applicable?)

30

4.2 Of these, how many are controls, if applicable?

0

4.3 If this is a multi-site study, how many participants do you anticipate will be enrolled in the entire study?

5.0 Justification for sample size:

Since this is a pilot study evaluating feasibility of our intervention and evaluation protocols, we will aim to enrol 30 patients. We will randomize 15 participants to each group. Thirty participants has been deemed acceptable to yield confidence intervals whose lower limits can help define the range of

plausible values for a subsequent power analysis. This will also provide adequate estimates of enrolment, follow-up rates, information on timing, and variance in our measurement protocol to inform a subsequent randomized controlled trial of the intervention.

4.3 Recruitment of Participants (Health)

1.0 Recruitment

* 1.1 How you will identify potential participants? Please be specific. (i.e. Will you be screening clinical lists, accessing electronic health records (e-clinician), asking staff from a particular area to let you know when a patient meets criteria, will you be sitting in the emergency department waiting room, etc?)

Recruitment will take place at the general surgical practice of [name] at the Fort Saskatchewan Community Hospital. Patients on the wait list for inguinal hernia repair surgery will be contacted by [name] administrative support staff. They will ask the participant if they are interested in participating in this study. If so, their contact information will be taken and provided to the study team who will then contact the individual to provide further study information and obtain informed consent.

1.2 If you are using patient/clinical records to identify potential participants for research purposes, will someone from the data custodian/clinical care team seek prior consent of the participant to allow the researcher to look at their records?

Yes	\bigcirc	No
103		140

1.3 Once you have identified a list of potentially eligible participants, indicate how the potential participants' names will be passed on to the researchers AND how will the potential participants be approached about the research.

The names and contact details of potentially eligible participants will be provided to the investigative team by the surgeon's research coordinators using a 'Consent to Contact' form that will be completed either at time of their examination by the surgeon or after they are on the wait list and contacted by the administrative support staff. If contacted over the phone, the consent to contact form will be emailed for signing. The investigators will then arrange a meeting (telephone or Zoom videoconference) with the potential participant to explain the study and provide an information sheet. Final consent to participate will be done over REDcap.

1.4 Outline any other means by which participants could be identified(e.g. response to advertising such as flyers, posters, ads in newspapers, websites, email, list serves, physicial or community organization referrals):

Not applicable since we require patients who have been scheduled for inguinal repair surgery.

2.0 **Pre-Existing Relationships**

2.1 Will potential participants be recruited through pre-existing relationships with researchers (e.g. Will an instructor recruit students from his classes, or a physician recruit patients from her practice? Other examples may be employees, acquaintances, own children or family members, etc)?

Yes No

2.2 If YES, identify the relationship between the researchers and participants that could compromise the freedom to decline (e.g. clinician/patient, professor/student):

If it is acceptable to the ethics board, Dr, [name] will recruit directly. However, we will have a research assistant make first contact with patients on [name] surgical wait list so that patients feel no obligation or coercion to participate in the study.

2.3 How will you ensure that there is no undue pressure on the potential participants to agree to the study?

Initial contact will be made by an administrative staff member to determine if the potential participants are interested.

Will your study involve any of the following (select all that apply)? 3.0 None of the above

4.5 Informed Consent Determination

1.0 Describe who will provide informed consent for this study(i.e. the participant, parent of child participant, substitute decision maker, no one will give consent – requesting a waiver) Each participant will provide informed consent for this study. Since the first session is in-person, we will complete the consent process and documentation in person. Although the participants may also be asked to complete the study demographic form and questionnaires via REDCap prior to that session (consent implied through completion).

1.1 Waiver of Consent Requested

If you are asking for a waiver of participant consent, please justify the waiver or alteration and explain how the study meets all of the criteria for the waiver. Refer to Article 3.7 of TCPS2 and provide justification for requesting a Waiver of Consent for ALL criteria (a-e) Not applicable.

1.2 Waiver of Consent in Individual Medical Emergency If you are asking for a waiver or alteration of participant consent in individual medical emergencies, please justify the waiver or alteration and explain how the study meets ALL of the criteria outlined in Article 3.8 of TCPS2 (a-f).

Not applicable.

2.0 How will consent be obtained/documented? Select all that apply Signed consent form

If you are not using a signed consent form, explain how the study information will be provided to the participant and how consent will be obtained/documented. Provide details for EACH of the options selected above:

- 3.0 Will every participant have the capacity to give fully informed consent on his/her own behalf?
 - Yes No
- 4.0 What assistance will be provided to participants or those consenting on their behalf, who may require additional assistance? (e.g. non-English speakers, visually impaired, etc.)
 The study team will meet with the participants to provide any assistance needed. However, due to the nature of this study any participants experiencing difficulty with the consent process will not be enrolled.
- * If at any time a PARTICIPANT wishes to withdraw from the study or from certain parts of the study, describe when and how this can be done.

Participants can withdraw at any time during the study. If requested, all electronic data will be deleted for those withdrawing.

- 6.0 Describe the circumstances and limitations of DATA withdrawal from the study, including the last point at which participant DATA can be withdrawn (i.e. 2 weeks after transcription of interview notes)

 Participants can withdraw from the study up to the point where analysis has been completed and results presented.
- 7.0 Will this study involve any group(s) where non-participants are present? For example, classroom research might involve groups which include participants and non-participants.
 - O Yes No

5.1 Data Collection

* Will the researcher or study team be able to identify any of the participants at any stage of the study?

- 2.0 Primary/raw data collected will be (check all that apply):
 All personal identifying information removed (anonymized)
- 3.0 If this study involves secondary use of data, list all original sources: Not applicable.
- 4.0 In research where total anonymity and confidentiality is sought but cannot be guaranteed (eg. where participants talk in a group) how will confidentiality be achieved?

 Not applicable.

5.2 Data Identifiers

* Personal Identifiers: will you be collecting - at any time during the study, including recruitment - any of the following (check all that apply):
 Surname and First Name
 Address

Full Postal Code
Telephone Number
Email Address

Age at time of data collection

2.0 Will you be collecting - at any time of the study, including recruitment of participants - any of the following (check all that apply):

There are no items to display

- * If you are collecting any of the above, provide a comprehensive rationale to explain why it is necessary to collect this information:

 Name and contact information will be used to recruit participants.

 Age at time of data collection is being collected to describe our sample.

 Address and postal code will be used to contact patients at follow-up.
- 4.0 If identifying information will be removed at some point, when and how will this be done?

Personal identifying information will not be removed, since we will need it to contact participants at follow-up.

* Specify what identifiable information will be RETAINED once data collection is complete, and explain why retention is necessary. Include the retention of master lists that link participant identifiers with deidentified data:

All patient names and contact information will be retrained in case we need to follow-up with patients about the study.

6.0 If applicable, describe your plans to link the data in this study with

data associated with other studies (e.g within a data repository) or with data belonging to another organization:

Not applicable.

5.3 Data Confidentiality and Privacy

* How will confidentiality of the data be maintained? Describe how the identity of participants will be protected both during and after research.

All investigators and graduate students working on this project will be trained in research ethics (CORE certification) and confidentiality issues. All data will be stored on password-protected and encrypted secure computers at the University of Alberta and McMaster University campuses. During presentations, we present group-level data and avoid providing individual identifiers.

2.0 How will the principal investigator ensure that all study personnel are aware of their responsibilities concerning participants' privacy and the confidentiality of their information?

All investigators and graduate students working on this project will be trained in research ethics (CORE certification) and confidentiality issues.

- 3.0 External Data Access
 - * 3.1 Will identifiable data be transferred or made available to persons or agencies outside the research team?
 - O Yes No

5.4 Data Storage, Retention, and Disposal

- * Describe how research data will be stored, e.g. digital files, hard copies, audio recordings, other. Specify the physical location and how it will be secured to protect confidentiality and privacy. (For example, study documents must be kept in a locked filing cabinet and computer files are encrypted, etc. Write N/A if not applicable to your research)

 All electronic data will be saved in a password protected, secure University of Alberta computer and network within a password protected Excel file. All physical documents will be stored in the Rehabilitation Research Centre ([name]) at the University of Alberta. Only the Co-Pls and their graduate students will have access to study data.
- 2.0 * University policy requires that you keep your data for a minimum of 5

years following completion of the study but there is no limit on data retention. Specify any plans for future use of the data. If the data will become part of a data repository or if this study involves the creation of a research database or registry for future research use, please provide details. (Write N/A if not applicable to your research)
We have no plans for future use of the data, but will keep all records and data for a period of 5 years at least.

3.0

If you plan to destroy your data, describe when and how this will be done? Indicate your plans for the destruction of the identifiers at the earliest opportunity consistent with the conduct of the research and/or clinical needs:

We have no plans for destroying our data.

Documentation

Add documents in this section according to the headers. Use Item 11.0 "Other Documents" for any material not specifically mentioned below.

Sample templates are available by clicking HERE.

1.0 Recruitment Materials:

Document Name		Version Date		Description
⊕	Consent to Contact form V2	0.03	2021-03-02 4:43 PM	
⊕ €	CLEAN Consent to Contact form V2	0.02	2021-03-03 9:01 AM	

2.0 Letter of Initial Contact:

Document Name Version Date Description

There are no items to display

- 3.0 Informed Consent / Information Document(s):
 - 3.1 What is the reading level of the Informed Consent Form(s):
 - 3.2 Informed Consent Form(s)/Information Document(s):

	Document Name		on Date	Description
ூ ↔	Letter of Information and Consent V2	0.05	2021-03- 02 4:43 PM	
	CLEAN Letter of		2021-03-	

Information and Consent 0.01 03 7:47 V2 AM

4.0 Assent Forms:

Document Name Version Date Description

There are no items to display

5.0 Questionnaires, Cover Letters, Surveys, Tests, Interview Scripts, etc.:

	Document Name	Versio	n Date	Description
ூ ↔	Assessment booklet V4.docx	0.03	2021-03-02 4:44 PM	
9	Feedback Survey	0.01	2021-03-02 4:44 PM	
9	Functional Testing Form	0.01	2021-03-02 4:45 PM	
9	Adherence and Adverse Events Form	0.01	2021-03-02 4:46 PM	
5	CLEAN Assessment booklet V4.docx	0.01	2021-03-03 7:48 AM	

6.0 Protocol/Research Proposal:

	Document Name		Date	Description
ூ ↔	Full proposal	0.04	2021-01-13 12:57 PM	
9	Data Collection Timeline and Protocol	0.01	2021-03-02 4:45 PM	
9	Exercise Protocol	0.01	2021-03-02 4:46 PM	

7.0 Investigator Brochures/Product Monographs:

Document Name Version Date Description

There are no items to display

8.0 Health Canada No Objection Letter (NOL):

Document Name Version Date Description

There are no items to display

9.0 Confidentiality Agreement:

Document Name Version Date Description

There are no items to display

10.0 Conflict of Interest:

Document Name Version Date Description

There are no items to display

11.0 Other Documents:

For example, Study Budget, Course Outline, or other documents not mentioned above

	Document Name	Version	Date	Description
9	Appendix with Feasibility Criteria	0.02	2021-01-13 12:25 PM	

Final Page

You have completed your ethics application! Click "Continue" to go to your workspace.

This action will NOT SUBMIT the application for review.

Only the Study Investigator can submit an application to the REB by selecting the "SUBMIT STUDY" under My Activities after you click CONTINUE.

APPENDIX 2

FEASIBILITY AND ACCEPTABILITY CRITERIA							
Proceed	Proceed with Protocol Amendments	Significant Amendments Required					
Recruitment							
n=30 within 4 months	n ≥ 15 within 8 months	n < 10 within 8 months					
50% of eligible participants consent to participate	40% of eligible participants consent to participate	25% of eligible participants consent to participate					
Exercise program							
60% of participants report exercise at least 3 times a week	40% of participants report exercise at least 3 times a week	25% of participants report exercise at least 3 times a week					
Content Acceptability							
50% found treatment useful (Likert ≥ 4/5)	25% found treatment useful (Likert ≥ 4/5)	< 25% found treatment useful (Likert ≥ 4/5)					
50% found treatment helpful (Likert ≥ 4/5)	25% found treatment helpful (Likert ≥ 4/5)	< 25% found treatment helpful (Likert ≥ 4/5)					
Format Acceptability							
50% found treatment delivery (in-person and home) acceptable (Likert ≥ 4/5)	25% found treatment delivery acceptable (Likert ≥ 4/5)	< 25% found treatment delivery acceptable (Likert ≥ 4/5)					
50% reported being likely to recommend this treatment	25% reported being likely to recommend this treatment	< 25% reported being likely to recommend this treatment					
50% reported being likely to use this treatment again	25% reported being likely to use this treatment again	< 25% reported being likely to use this treatment again					

Follow Up						
90% of participants followed up at the end of Prehab	50% of participants followed up at the end of Prehab	25% of participants followed up at the end of Prehab				
80% of participants followed up at 3 months	50% of participants followed up at 3 months	25% of participants followed up at 3 months				
Treatment						
70% of participants attended all treatment sessions	50% of participants attended all treatment sessions	25% of participants attended all treatment sessions				
70% of sessions were compatible with participant's work/activity schedule	50% of sessions were compatible with participant's work/activity schedule	25% of sessions were compatible with participant's work/activity schedule				
Burden						
75% of participants found the burden of completing questionnaires Likert <3/10 (0 = no burden, 10 = most burden)	50% of participants found the burden of completing questionnaires Likert <3/10 (0 = no burden, 10 = most burden)	25% of participants found the burden of completing questionnaires Likert <3/10 (0 = no burden, 10 = most burden)				
Adverse Events						
No adverse event	1 adverse event related to re- injury	2 or more adverse events

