2.1 Study Objectives and Design

1.0 * Provide a lay summary of your proposed research which would be understandable to general public

Inguinal hernia repair is one of the most common surgeries, with more than 20 million performed globally each year. It is estimated that approximately 15% of patients undergoing inguinal hernia repair will experience persistent post-surgical pain that could last months to years. Evidence from related procedures indicates that better surgical preparation through pre-operative exercise and education (i.e. Prehabilitation) followed by ongoing post-surgical rehabilitation leads to more rapid recovery, return to activities and lower likelihood of persistent post-surgical pain. We will determine the feasibility of a peri-operative rehabilitation program (pre- and post-surgery)

and our study protocol for patients undergoing inguinal hernia repair surgery. We hypothesize that: 1) our peri-operative intervention will be feasible and safe to undertake within a clinical setting; 2) we will enrol adequate numbers to justify a larger trial; and that 3) our outcome measurement protocol will provide meaningful information with high response rate and low attrition after 3 months.

Implications

This study is novel and timely given the current healthcare focus on improving strategies for the prevention of chronic pain. The obvious potential benefits for patients with inguinal hernia is the development of a program with the potential to improve post-surgical outcomes and reduce likelihood of post-surgical pain. Our findings will inform a larger, multicenter clinical trial to evaluate this intervention approach in patients undergoing inguinal hernia repair.

2.0 * Provide a full description of your research proposal outlining the following:

- Purpose
- Hypothesis
- Justification
- Objectives
- Research Method/Procedures
- Plan for Data Analysis

Purpose

The aim of the proposed project is to determine the feasibility of a perioperative rehabilitation program (pre- and post-surgery) and our study protocol for patients undergoing inguinal hernia repair surgery. We will answer the following question: Is a study of a peri-operative rehabilitation program feasible in terms of recruitment rate, treatment adherence, timelines, data collection procedures, patient follow-up and resources required?

Hypothesis

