Sample - We will recruit patients referred to general surgery for an elective inguinal hernia repair within Alberta Health Services – Fort Saskatchewan Community Hospital ([name] clinic). Patients meeting the inclusion criteria will be randomized 1:1 to either undergo 6 weeks of prehabilitation exercises + post-surgical follow-up or else usual care. Inclusion criteria include: 1) scheduled to undergo first-time inguinal hernia repair surgery after a physical examination identified signs and symptoms consistent with inguinal hernia (direct or indirect hernia); 2) willingness to participate in a targeted perioperative exercise program; 3) 18+ years of age; 4) no medical contraindications to participation in exercise; and 5) employed full-time and required to lift at least 10kg at work. Specific contra-indications that will be screened for include associated medical conditions that preclude exercise. This includes uncontrolled medical conditions including diabetes, hypertension, vertigo, congestive heart failure, chronic obstructive pulmonary disease, intra-abdominal ascites, or pre-existing malnutrition. We will also screen for previous recurrence of hernia, use of narcotics, bone and joint conditions of the spine or extremities, or history of other abdominal surgeries, which will be exclusionary criteria for the study. Exclusion criteria include: 1) previous inguinal hernia; and 2) Body Mass Index >35 since morbidly obese patients experience more surgical complications.[13]

Sample Size - Since this is a pilot study evaluating feasibility of our intervention and evaluation protocols, we will aim to enrol 30 patients. We will randomize 15 to both the intervention and control groups. Thirty participants has been deemed acceptable to yield confidence intervals whose lower limits can help define the range of plausible values for a subsequent power analysis.[14] This will also provide adequate estimates of enrolment, follow-up rates, information on timing, and variance in our measurement protocol to inform a subsequent randomized controlled trial of the intervention.

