Intervention Description - The perioperative rehabilitation program will include an established set of structured exercises aimed at core strengthening and individualized activity-based functional training in preand post- operative stages. We will follow a traditional occupational rehabilitation approach, focusing exercise training on activities that the patient is experiencing difficulty with due to the hernia. The exercise program is described in more detail in the attached 'hernia exercise protocol' document. The program will be delivered by a physiotherapist and a trained exercise therapist. This includes the sessions that will be done in person as well as those that will be done virtually. Education that will be provided includes basic information about inguinal hernia and the surgical repair technique, what to expect in the days and weeks following surgery, advice for post-operative recovery, importance of activity and exercise to recovery, pain coping strategies and techniques for reducing risk of hernia recurrence. Education will be provided in person by the surgeon and study team, as well as through YouTube videos that provide more standardized information. Education that will be provided includes basic information about inguinal hernia and the surgical repair technique, what to expect in the days and weeks following surgery, advice for post-operative recovery, importance of activity and exercise to recovery, pain coping strategies and techniques for reducing risk of hernia recurrence.

Measures – In additional to demographic and occupational information, we will collect feasibility and clinical outcomes. Feasibility outcomes are: 1) recruitment rate expressed as the average number of patients referred to the study per week and the number of participants enrolled in the program; 2) patient adherence to the program; 3) acceptability of program content; 4); acceptability and compliance with study questionnaires; 5) follow-up rates; and 6) serious adverse events. A priori criteria for the feasibility outcomes are presented in the Appendix.

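### The consent-rate criterion is set on eligible patients, but willingness to exercise is itself an eligibility criterion; read literally, the rate omits programme refusals and can overstate uptake

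*Combined protocol and SAP*

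**What the plan says.** Appendix 2 has two recruitment rows. One is a count against time. The other is a consent rate, whose top tier is "50% of eligible participants consent to participate"; the two lower tiers, 40% and 25%, use the same denominator. The Plan for Data Analysis in section 2.1 says that the feasibility targets are judged against this appendix.

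Eligibility is defined twice, and willingness is inclusion criterion 2 each time: "willingness to participate in a targeted perioperative exercise program" in section 2.1 (Sample) and "willingness to participate in a 6-week targeted exercise program" in section 4.2. Nothing supplied gives a separate meaning of 'eligible' for the consent row.

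On first contact, section 4.3 item 1.1 says of the surgeon's administrative staff: "They will ask the participant if they are interested in participating in this study. If so, their contact information will be taken". Item 2.3 agrees: "Initial contact will be made by an administrative staff member to determine if the potential participants are interested". Item 2.2, however, gives first contact to a research assistant and leaves open direct recruitment by the surgeon if the ethics board accepts it. Item 1.3 allows the contact form to be completed at the surgeon's examination or after a later call.

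Section 2.1 (Measures) defines the recruitment outcome as "recruitment rate expressed as the average number of patients referred to the study per week and the number of participants enrolled in the program". It lists neither patients approached nor patients declining.

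**The concern.** A consent rate is useful for planning if its denominator holds everyone who could have joined and was asked. Here one reason for saying no, not wanting the exercise programme, is also a reason for being ineligible. Applied as written, the rule removes those refusals from the rate instead of counting them against it. Refusals at first contact may be lost as well, because patients who are not interested are not passed to the study team and the listed recruitment measures start at referral.

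Recruitment heads the study question, which asks whether the trial is "feasible in terms of recruitment rate, treatment adherence, timelines" and so on, and the Sample Size paragraph expects the pilot to supply enrolment estimates for the larger trial. An inflated rate would understate how many wait-list patients must be approached per participant, and could lift this row into a better tier. Most of the percentage rows on exercise, acceptability, attendance and burden can be answered only by people who joined. The consent rate is where patients who reject the programme could show up.

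**Working it through.** **Plan's own figure.** The 50%, 40% and 25% levels are pre-set thresholds with no derivation, so there is nothing to reproduce. What can be checked is the direction of the effect and how its size depends on an unknown share.

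**Inputs from the documents.** Tiers of 50%, 40% and 25% of eligible patients (Appendix 2); willingness as inclusion criterion 2 (sections 2.1 and 4.2); 30 participants planned (section 2.1).

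**Input not in the documents.** The share of clinically eligible patients filtered out of the denominator, f. Every value of f below is an assumption.

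**Direction.** Let E be the patients approached who meet every criterion other than willingness, W those of E who remain in the denominator, and C those who consent. C lies within W and W within E, so

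C/W ≥ C/E.

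The two are equal only if nobody is filtered out (W = E) or nobody consents. Enumerating every combination up to E = 60 gave no exception.

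**Size as a share.** With true uptake U = C/E and f = 1 − W/E, the reported rate is U/(1 − f).

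| True uptake | f = 0 | f = 10% | f = 20% | f = 40% |
|---|---|---|---|---|
| 40% | 40% | 0.40/0.90 = 44.4% | 0.40/0.80 = 50% | – |
| 30% | 30% | 0.30/0.90 = 33.3% | 0.30/0.80 = 37.5% | 0.30/0.60 = 50% |

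A true 40%, the middle tier, reaches the top tier at f = 20%.

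**Size as counts.** Take 30 consents and a reported 50%, that is 30 of 60. With k uncounted refusals, true uptake is 30/(60 + k):

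- k = 0: 30/60 = 50%
- k = 5: 30/65 = 46.2%
- k = 15: 30/75 = 40%
- k = 40: 30/100 = 30%

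**Planning consequence.** Patients to approach for 30 participants, taking consent as enrolment: 30/0.50 = 60 if the reported rate is believed, against 30/0.40 = 75 at a true 40% and 30/0.30 = 100 at a true 30%.

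**The case against.** The strongest reply is that the team may not read 'eligible' literally. Willingness is learned only by asking, so a patient who is asked and says no can naturally be recorded as not consenting. Nothing in the documents says that such a patient is logged as ineligible. This stands: if that is the practice, the willingness criterion causes no bias. But the supplied text does not say so, and the literal rule leads the other way.

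A reader might infer from "The names and contact details of potentially eligible participants will be provided to the investigative team" (section 4.3 item 1.3) that eligibility is settled only after the interest question, so that early refusals are certainly lost. The documents do not support this. The phrase echoes the form's own prompt, in which the list comes before the approach. The contact form may be completed at the surgeon's examination, when the hernia criterion can already be known, and a research assistant who made first contact could see refusals directly. Loss at this step is possible, not shown.

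The unsupplied attachments (the full proposal, the data-collection timeline and the contact form) could define the denominator or provide a log. That stands too, and the fix allows for it.

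It is also fair that the size is wholly assumed. At 30 of 60 the 95% Wilson interval is about 38% to 62%, so a handful of uncounted refusals is small beside sampling error. But that interval is centred on the reported rate and does not allow for refusals left out of it.

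Finally, the target of 30 patients in 4 months does not use this denominator. True, but that row measures speed and cannot show how many patients must be approached per enrolment.

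**Conclusion.** The point holds as a conditional one. Under the literal reading of Appendix 2 with the inclusion criteria, the consent rate can only equal or exceed uptake among clinically eligible patients approached. The direction is certain under that reading; the size is unknown and could be small or nil. A shift of one tier (a true 40% reported as 50%) needs 20% of clinically eligible patients to be filtered out, or 15 uncounted refusals beside 30 of 60. Neither figure is documented.

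Two stronger conclusions should not be drawn. The criterion is not circular: a willing patient can still decline randomisation or the questionnaires, and that refusal stays in the denominator. Nor is the recruitment assessment as a whole undermined: one row is affected, the count-against-time row is not, and Appendix 2 gives no rule for combining rows.

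It is still worth fixing, because the rate feeds a headline feasibility outcome and refusals that are not logged may be impossible to recover later.

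**What to change.** In Appendix 2, define the consent-rate denominator as all patients approached who meet inclusion criteria 1, 3, 4 and 5 and have no exclusion, leaving out criterion 2. Count both lack of interest and unwillingness to exercise as non-consent. Criterion 2 stays in force for randomisation; only the denominator changes.

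Reconcile section 4.3 items 1.1, 2.2 and 2.3 on who makes first contact. Have that person (administrative staff, research assistant or surgeon) keep an anonymous tally of patients approached, patients declining and the reason, or cite the existing attachment that does this.

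Some patients will decline before their work, lifting or medical status is checked. Report the rate with these patients counted out and counted in. For example, 30 consents, 60 patients checked and 15 unchecked refusals give 30/60 = 50% and 30/75 = 40%. The rate among the clinically eligible lies between the two. State in advance which of them is compared with the tiers, so that the row still gives a single answer.

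The cost is some appendix wording, a small tally task at a contact that already takes place, and a consent rate that may look less favourable or have to be shown as a range.
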